CLINICAL STUDY PROTOCOL

C. Kenneth and Dianne Wright
Center for Clinical and Translational Research

SAFEty Study of Early Infusion of Vitamin C for Treatment of Novel Coronavirus Acute Lung Injury

(SAFE EVICT CORONA-ALI)

Protocol Version: 1.83

Protocol Version IRB approved: 08/10/2021

VCU IRB Number: HM20018977

ClinicalTrials.gov Identifier: NCT04344184

IND: 149518

Study Personnel

Principal Investigator(s) [name]
Virginia Commonwealth University
Department of Internal Medicine
Pulmonary and Critical Care Medicine

[name], MD
Virginia Commonwealth University
Department of Internal Medicine
Pulmonary and Critical Care Medicine

Co-Investigators
[name]
Central Virginia VA Health System
Department of Internal Medicine
Gastroenterology and Hepatology Division

[name]
Department of Biostatistics
Virginia Commonwealth University,
Massey Cancer Institute

[name]
Virginia Commonwealth University
Department of Surgery
Division of Trauma Surgery

[name]
Virginia Commonwealth University
Department of Surgery
Division of Trauma Surgery

Clinical Coordinators: [name] and [name]
Virginia Commonwealth University
Department of Internal Medicine
Pulmonary and Critical Care Medicine

Regulatory Contact: [name]
Virginia Commonwealth University
Department of Internal Medicine
Pulmonary and Critical Care Medicine

Synopsis

Study Description

The purpose of this proof-of-concept, phase 2 safety study is to examine the safety profile, and possible therapeutic effects of high-dose, intravenous vitamin C (HDIVC) compared to placebo in hospitalized adult patients with novel Coronavirus COVID-19 and hypoxemia.

Objectives

To assess the safety profile of a 4-day (96-hour) intravenous vitamin C treatment protocol (comprised of four intravenous infusions a day, that is 50 mg/kg every 6 hours) in patients with laboratory-confirmed SARS-CoV-2 infection manifesting COVID-19 (Novel Coronavirus Disease 2019) with hypoxemia. While performing this phase 2 proof-of-concept, safety study, we will explore the following hypotheses:

Endpoint

Primary Endpoint (Safety): HDIVC infusion does not worsen the patients' outcomes, as measured by differences in the mean 9-point (from 0 to 8) World Health Organization (WHO) ordinal scale for disease improvement, between the two populations at 28, 60 and 90 days:

Table 1.

Patient State	Descriptor	Score
Uninfected	No clinical or virologic evidence of infection	0
Ambulatory	No limitation of activities	1

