S = standard of care (when feasible), R = research (optional), RS: research specific including phlebotomy; BMP = basic metabolic profile, DNR = do not resuscitate, ECMO = Extracorporeal membrane oxygenation, iNO = inhaled nitric oxide, AKI = acute kidney injury, CRRT = Continuous renal replacement therapy (continuous dialysis), HD = Hemodialysis, CKD = Chronic kidney disease, CRP = C Reactive Protein, ABG = Arterial blood gas, CAM-ICU = ICU Delirium scale, IL-6 = Interleukin 6, afib = atrial fibrillation, aflutter = atrial flutter, SVT = Supraventricular Tachycardia, AST = Aspartate aminotransferase, ALT = Alanine aminotransferase, ALP = Alkaline phosphatase.								
R* IF the patient is in the hospital								
R7 only on day 7 within that interval								
R14 only on day 14 within that interval								
R21 only on day 21 within that interval								
R28 only on day 28 within that interval								
R14^{AKI} collect on day 14 if patient develops AKI and still in the hospital								
R21^{AKI} collect on day 21 if patient develops AKI and still in the hospital								
R28^{AKI} collect on day 28 if patient develops AKI and still in the hospital								
End of Study Definition								
Treatment protocol will continue for 4 days (96 hours), and, if needed, the last study-specific bloodwork will be collected on day 7. Study will end if patient is withdrawn from the study, or lost to follow-up. All subjects will be followed to day 28 for collection of clinical outcomes data through electronic health records (EHR) even though the treatment protocol will be completed by 96 hours from randomization at the latest. Secondary outcome data will be collected either during in-person (clinic) visit or via telephone at the 90-day follow-up. Only acceptable reasons for early study termination include consent withdrawal or loss to follow-up.								

Abbreviations

Abbreviation	Explanation
AE	Adverse Event
AKI	Acute Kidney Injury
ARDS	Acute Respiratory Distress Syndrome
Case Report Form	Case Report Form
CDC	Centers for Disease Control
CFR	Code of Federal Regulations
CLIA	Clinical Laboratory Improvement Amendments
CMP	Clinical Monitoring Plan
CONSORT	Consolidated Standards of Reporting Trials
COVID-19	Coronavirus Disease 2019
D5W	Dextrose 5% Water
DHHS	Department of Health and Human Services
DRE	Disease-Related Event
DSMB	Data Safety Monitoring Board
eCRF	Electronic Case Report Form
ED	Emergency Department
FIP	Feces-Induced Peritonitis
HDIVC	High-Dose Intravenous Vitamin C

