4.2 Scientific Rationale for Study Design

The purpose of this study is to assess the safety, tolerability, efficacy of intravenously infused ascorbic acid therapy for patients with COVID19 and decreased oxygenation. **This study will provide an opportunity to explore specifically the specific safety of high-dose intravenous vitamin c and explore the hypothesis generated by case reports, that high-dose vitamin C has clinically significant adverse effects on the kidneys.** By administering the infusion at the first objective sign of worsening oxygenation, documented by Pulse Oximetry Saturation(SpO₂)/Fraction of Inspired Oxygen (FiO₂) – that is the S/F ratio, decreased pulse oximetry at baseline, HDIVC may reduce the inflammatory process and development of respiratory failure requiring intubation, which is critical in a pandemic when ventilators, ICU beds, and medical staff may be in short supply.

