Therefore, this proof-of-concept study of 60 patients, 30 allocated to the treatment arm and 30 to the placebo arm, will have 96% power (1-beta (β)) to detect an **average of 1-point difference** in the primary outcome, the WHO COVID-19 ordinal scale, with an alpha error probability (α) of 4% (0.04). This is by applying a two-tail, t-test with unequal variances (see figure below).

[figure not shown]

For binary secondary outcomes, we plan to use the chi-squared test, with 1-degree of freedom. The expected effect size for an alpha level of 0.05 and power of 80% is 0.36, as shown in the figure below.

In contrast, for a constant hypothetical effect size of 0.2, a phase 3 trial will require at least 200 patients to achieve a power of 80% and an alpha of 0.05 (yellow line, figure below).

Planned Interim Analyses:

No planned interim analyses will be conducted in this study. The results will be analyzed after the 60th patient has finished enrollment and has been discharged from the hospital (phase 1). There are no provisions to stop the trial early for efficacy.

Missing Data

The primary outcome, the WHO-COVID-19 scale is encompassing missing data from death or hospital discharge. Missing laboratory or clinical data due to patient death, or discharge will not be imputed given this practice will introduce systematic bias, since they are not missing at-random. For organ-system data, the highest scores will be attributed after patient death, since death causes cessation of all organ function, and any imputation method will underestimate the severity. For missing-at-random data, multiple imputation with a pattern-mixture model with control-based pattern imputation will be used, with 50 imputed data sets, in order to compensate for data that may be missing at random.

10 - Supporting Documentation and Operational Considerations

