10.1.8 Quality Assurance and Quality Control

Quality control (QC) procedures will be implemented beginning with the data entry system and data QC checks that will be run on the database will be generated. Any missing data or data anomalies will be communicated to the site(s) for clarification/resolution. As mentioned in the statistical section 9.5, for missing at random data, we will employ imputation methods that may include multiple imputations, or pattern mixture models, depending on the appropriateness of each scenario.

Following written Standard Operating Procedures (SOPs), the monitors will verify that the clinical trial is conducted and data are generated and biological specimens are collected, documented (recorded), and reported in compliance with the protocol, International Conference on Harmonisation Good Clinical Practice (ICH GCP), and applicable regulatory requirements (e.g., Good Laboratory Practices (GLP), Good Manufacturing Practices (GMP)).

The investigational site will provide direct access to all trial-related sites, source data/documents, and reports for the purpose of inspection by local and regulatory authorities.

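### Control-based imputation is assigned to data called missing at random, and it pulls imputed vitamin C outcomes toward placebo in a trial that asks about harm

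*Combined protocol and SAP*

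**What the plan says.** Section 9, Missing Data, sets out three rules.

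- On the primary scale: "The primary outcome, the WHO-COVID-19 scale is encompassing missing data from death or hospital discharge". Death scores 8 on that scale.
- On other data: "Missing laboratory or clinical data due to patient death, or discharge will not be imputed". Organ-system data take the worst score after death.
- For the rest: "For missing-at-random data, multiple imputation with a pattern-mixture model with control-based pattern imputation will be used, with 50 imputed data sets". The control-based variant is not named, and neither are the variables or time points it applies to.

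Section 10.1.8 returns to data missing at random and says "we will employ imputation methods that may include multiple imputations, or pattern mixture models, depending on the appropriateness of each scenario". It does not mention the control-based form. Neither place names a sensitivity analysis.

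The Synopsis words the primary safety endpoint as "HDIVC infusion does not worsen the patients", followed by their outcomes on the 9-point WHO scale at days 28, 60 and 90. Section 9 tests it with a two-sided unequal-variance t-test and states no margin. On leaving the study, the Synopsis says "Only acceptable reasons for early study termination include consent withdrawal or loss to follow-up", and sections 4.1 and 4.4 say much the same. Section 9, Model Set-Up, labels the arms A and B and reveals the interventions only once the statistical analysis is complete.

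**The concern.** Control-based imputation models a missing treated patient on the placebo arm. When a trial sets out to show benefit, that is a deliberate handicap on the treatment. When the question is whether the treatment does harm, the same step narrows the gap between the arms and makes the treatment look safer.

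The label adds to the problem. If the data are missing at random, the matching method imputes each patient from the same randomized arm and from the patient's own observed history. Borrowing from the other arm assumes that missing vitamin C patients behave unlike observed vitamin C patients, which is a missing-not-at-random assumption.

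The test is for a difference, with no margin, so a non-significant result is the one likely to be read as reassuring. A rule that shrinks the difference makes that result more likely, and no planned analysis would show how far the conclusion rested on imputed, placebo-like scores.

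There is also a practical conflict. The method cannot run without knowing which arm is control, yet section 9 withholds that until the analysis is finished.

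**Working it through.** **Which data reach the rule.** The plan does not list them, so this is inference. Deaths score 8. Laboratory and clinical values missing through death or discharge are not imputed. Patients who only stop the drug remain under observation (sections 7.1 and 8.2.1). Outcomes to day 28 come from chart review (section 4.4). What remains is mainly WHO scores missing after consent withdrawal or loss to follow-up. The exposure is greatest at days 60 and 90, which are assessed by clinic visit or telephone (section 4.4).

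**The plan's own figure.** Section 9 gives 30 per arm, a 1-point difference, two-sided alpha 0.04 and power 96%. The text gives no SD. With SD = 1 (assumed), the noncentrality is 1 / (1 × √(2/30)) = 3.87 on 58 degrees of freedom, and the t-test power is 0.9598. The stated 96% is reproduced; the SD that gives exactly 96% is 0.999.

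**Shrinkage of the estimate.** Let p be the share of the vitamin C arm that is imputed. If those values take the placebo mean, the expected difference is (1 − p) × true difference. For a true harm of 1.0 point:

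- 1 of 30 missing: 1 − 0.033 = 0.97
- 2 of 30 missing: 1 − 0.067 = 0.93
- 10% missing (3 of 30, assumed): 0.90
- 20% missing (6 of 30, assumed): 0.80

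This shrinkage does not depend on the SD. The formula assumes that the model uses none of the patient's own post-baseline scores.

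**Effect on power.** Putting the shrunken difference into the same t-test at SD 1 lowers power from 96% to 91% (p = 10%) or 84% (p = 20%). A simulation then added imputation uncertainty. It used 2,000 trials per cell, normal outcomes, the same share missing completely at random in both arms, 50 imputations, Rubin's rules and no earlier scores in the model. Simulation error is about 1 point.

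| Missing per arm (assumed) | Own-arm imputation: mean estimate, power | Control-based: mean estimate, power |
|---|---|---|
| 10%, SD 1 | 1.00, 94% | 0.91, 91% |
| 20%, SD 1 | 0.99, 90% | 0.80, 75% |
| 10%, SD 2 | 1.01, 40% | 0.89, 30% |
| 20%, SD 2 | 1.02, 36% | 0.80, 17% |

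At 20% missing and SD 1, the choice of method alone costs 90 − 75 = 15 points of power to detect harm.

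**What own-arm imputation does not cover.** Let d_obs be the harm among observed patients and d_miss the harm among missing ones. The full-sample truth is (1 − p)·d_obs + p·d_miss. Control-based imputation returns (1 − p)·d_obs and falls short by p·d_miss. Own-arm imputation returns d_obs and falls short by p·(d_miss − d_obs). That is zero if missing patients resemble the rest of their arm, but positive if they left because they were harmed. A delta adjustment is therefore needed as well.

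**The case against.** The case against rests on scope and size, and much of it stands.

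- A reader might infer that a patient who cannot tolerate the drug is counted as a placebo patient. The documents do not support that. Section 7.1 separates stopping the drug from leaving the study, and section 8.2.1 continues monitoring after a grade 3 event. Such patients keep observed outcomes unless they also withdraw consent or are lost.
- A reader might take it as settled that every withdrawal or loss goes to this rule. Section 9 names neither. A discharged patient who cannot be reached at day 60 or 90 might be treated as missing through discharge or as missing at random; the text leaves this open.
- A reader might extend the point to the kidney question, since section 4.2 says the trial will "explore the hypothesis generated by case reports, that high-dose vitamin C has clinically significant adverse effects on the kidneys". Little renal data would reach the rule. Biomarkers are collected mainly on days 0 to 7, AKI is assessed in hospital, and values missing through death or discharge are not imputed.
- Rates of 10% to 20% have no source in the documents and look unlikely at day 28. A variant that uses earlier daily scores would shrink the difference less than (1 − p).
- Section 10.1.8 could be read as a competing method. It points back to the statistical section and lists elements of the same approach, so it is looser wording, not clearly a different rule.
- The study also looks at possible therapeutic effects, for which control-based imputation is cautious. Harm detection does not rest on this rule alone either: the DSMB reviews serious adverse events narratively (section 4.1), with monthly reviews proposed (section 10.1.5).

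These points limit the size of the bias and the certainty about its reach. They do not change its direction or remove the mismatch between label and method.

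**Conclusion.** The point holds in this form and should be fixed. Section 9 pairs a missing-at-random label with a missing-not-at-random method. For a primary endpoint about worsening, that method errs toward reassurance, and no planned analysis would reveal it.

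The size is probably small at day 28: with 1 or 2 of 30 vitamin C patients imputed, a 1.0-point harm would appear as 0.97 or 0.93. It could matter more at days 60 and 90, at 0.90 or 0.80 for 10% or 20% missing. These figures assume imputation at the placebo mean without the patient's earlier scores, and missing patients whose harm equals that of the rest of their arm. On those assumptions they are near the most the method can shrink the estimate. The missing rates are assumptions, and the power figures also rest on an assumed SD.

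The documents do not support the stronger conclusion that the safety result would be overturned or that harm would go undetected. The scope is inferred, and the main safety exits from treatment keep patients under observation.

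**What to change.** In section 9, Missing Data:

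1. State which variables, time points and reasons for missingness the imputation covers. Include discharged patients who cannot be reached at days 60 and 90.
2. Make multiple imputation within the randomized arm, under missing at random, the main method. Use WHO stratum, site and the patient's earlier WHO scores. This runs on masked A and B labels.
3. Add a delta-adjusted tipping-point analysis that makes missing vitamin C outcomes progressively worse until the conclusion changes. This is essential, because step 2 does not cover withdrawal caused by harm. To keep the labels masked, apply the adjustment to each group in turn and read off the relevant one after unmasking.
4. Keep control-based imputation, if at all, only as a sensitivity analysis for a claim of benefit. Name the variant, and say who runs it and when the control arm is identified.
5. Make section 10.1.8 refer to this rule in place of a choice by scenario.

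The cost is analysis wording and a little programming. The downside is a possibly less reassuring safety estimate. Conduct, dosing and sample size are unaffected.

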10.1 Regulatory, Ethical, and Study Oversight Considerations

10.1.1 Informed Consent Process

Consent forms describing in detail the study intervention, study procedures, and risks are given to the participant. Due to the infectious nature of COVID-19, we will follow the [FDA guidance](#) dated March 2020 and updated May 12, 2020, to obtain informed consent. In order to protect members of the research team the consent process will be conducted verbally using the existing the same remote system currently being used in the hospital for communication with patients regarding their clinical care. If the participant agrees to participate in the study, their consent will be documented either using an electronic signature, a wet signature which is photographed, attestation by an impartial witness and the investigator that the participant consented, or sterilization of the paper consent. Informed consent will be documented in the EHR prior to starting intervention/administering study intervention.

Informed consent is a process that is initiated prior to the individual's agreeing to participate in the study and continues throughout the individual's study participation. Consent forms will be Institutional Review Board (IRB) approved and the participant will be asked to read and review the document. The investigator will explain the research study to the participant and answer any questions that may arise. A verbal explanation will be provided in terms suited to the participant's comprehension of the purposes, procedures, and potential risks of the study and of their rights as research participants. Participants will have the opportunity to carefully review the written consent form and ask questions prior to consenting. However, given the time sensitive nature, participants will be given a maximum of 4 hours to make a decision. The participants should have the opportunity to discuss the study with their family or surrogates or think about it prior to agreeing to participate.

The participant will provide informed consent prior to any procedures being done specifically for the study. Participants will be informed that participation is voluntary and that they may withdraw from the study at any time, without prejudice. Participants will be informed of other COVID-19 trials that are being performed. Should another drug become available to treat COVID-19 that is safe and effective the drug to subjects enrolled in this trial will be offered. A copy of the informed consent document will be given to the participants for their records. The informed consent process will be conducted and documented in the source document (including the date) and consent provided before the participant undergoes any study-specific procedures. The rights and welfare of the participants will be protected by emphasizing to them that the quality of their medical care will not be adversely affected if they decline to participate in this study.

Some of the patients approached for participation in this research protocol will have limitations of decision-making abilities due to their critical illness. Hence, some patients will not be able to provide informed consent. Accordingly, informed consent will be sought from the potential subject's legally authorized representative (LAR) in compliance with Federal Regulations 45 CFR part 46. Only those individuals who are authorized to serve as LARs per [VCU IRB Written Policies and Procedures #XI-3](#) will be eligible to provide consent on behavior of patients to participate in this study. Because all participants are inpatients in the hospital, the study will use the same LARs for research consent as are acting as LARs for the purposes of treatment.

10.1.1.b Informed Consent with DocuSign Part 11

In concordance with the latest FDA guidance on consent purposes, the study is offering electronic Informed Consent. This will be offered through DocuSign Part 11. The consent forms will be identical in Spanish and English; however, the signatures will be electronic. The electronic informed consent (eIC) will **only be offered** to Legally Authorized Representatives (LAR) **and not in face-to-face consent with patients. For face-to-face encounters only the paper consent forms will be used.**

The consents will be offered in order to facilitate the following:

- Legally Authorized Representative (LAR) may not be able to travel on site in a timely manner.
- LAR may not be comfortable visiting the hospital
- LAR may not be adherent to social distancing/ face masks which make it impossible for study personnel to interact.

The following elements will be followed for the informed consent process, in concordance with the VCU IRB requirements:

- a) A remote discussion is required prior to sending the DocuSign Part 11 consent
- b) The consent will be emailed or faxed for the LAR to review **prior** to the discussion
- c) DocuSign consent cannot be used for in-person interactions. Only the paper ICF.
- d) A remote consent discussion is held via phone, Zoom, etc. and the LAR's questions are answered.
- e) If the person indicates they are willing, the study team member collects the person's name and email address.
- f) The study team member goes into their Part 11 DocuSign account, creates an envelope, and sends it to the participant. An access code will also be set and communicated to the LAR.
- g) The LAR clicks the DocuSign email and creates an account password to log in.
- h) They review and sign the consent document electronically.
- i) The DocuSign envelope is routed to the person obtaining consent for signature and then to the Principal Investigator.
- j) Once all signatures are obtained, all persons receive an email and can download a copy of the signed form.
- k) The study team (PI, regulatory contact) ensure that the DocuSign Part 11 consent is accessible any time an auditing is requested and a physical copy is held in the study's regulatory binder in a dedicated section of DocuSign Part 11 Informed Consents.

